3.1.4 Secondary Endpoints

Secondary endpoints include the following:

- PFS rate, defined as the time from registration to the time of disease progression or relapse (according to RECIST 1.1 only) or death, or the date of last tumor assessment without any such event (censored observation)
- PK profile APR-246 and concentration in plasma

- Cardiac profile of APR-246 and concentration of PLD
- The safety profile (adverse events [AEs], laboratory assessments, physical findings and biomarkers) of APR 246 and PLD chemotherapy
- Duration of response (complete or partial response)
- Progression-free survival (PFS) by assessment of CA-125
- Evaluation of potential biomarkers
- Biological activity in tumor and surrogate tissues.

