4.0 STUDY DESIGN

4.1 Overview of Study Design

This study is an open-label, multicenter phase II study to assess whether patients with platinum-resistant TP53-mutated HGSOC will benefit from treatment with APR-246 and PLD chemotherapy. At least 25 evaluable patients will be included in this study. Patients may continue to receive treatment for as long as they are benefiting from it.

Different APR-246 infusion times will be explored. The Main Study will assess the standard 6 hour APR-246 infusion whilst the Sub-Study will explore shorter infusions (3 or 4 hour).

All patients will have pre-screening IHC to determine p53 status and therefore eligibility. Archived sections from the original tumor sample will be reviewed by a gynecological pathologist to confirm the diagnosis of HGSOC and positive IHC staining for p53. Patients without positive p53 staining will not be included.

Patients will receive standard 6 hour APR-246 infusion (fixed dose of 4.5 g APR-246) and PLD chemotherapy. After evaluation of the first six patients with the standard 6 hour infusion, a subgroup of up to 25 additional patients will be given the APR-246 dose over a shorter infusion time in order to evaluate this dosing schedule according to the same criteria as in the main study. The sub-study will be conducted in parallel with the main study.

At follow-up visits after the end of treatment, radiological tumor assessments should be performed every 8 weeks until protocol-defined progression occurs. For patients with stable disease, follow-up will take place until disease progression or until death.

All scans for each individual patient should have the same modality (CT or MRI) but CT is preferred.

A safety review committee (SRC) will evaluate the first 6 patients who receive the standard 6 hour infusion and the first 6 patients in the sub-study, to determine whether further patients can be enrolled and receive the same APR-246 infusion duration, at the same dose.

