6.6 Concomitant Treatment and Prohibited Medication

Patients are allowed to receive supportive care therapies (including cytokine growth factors) concomitantly during the trial.

No anti-cancer therapy other than that given in this clinical trial; no immunotherapy; no hormonal cancer therapy; no radiation therapy (except palliative); and no experimental medications are permitted during the trial. No PARP inhibitors are permitted after a beneficial response to study therapy.

Radiation therapy to index lesions should be avoided where possible; when deemed essential for patient well-being, the sponsor must be informed as the patient will become non-evaluable for endpoints assessed by RECIST, i.e. response rate and PFS.

Concomitant use of paracetamol-based compounds is allowed. However, caution should be taken when co-administering APR-246 with high doses of paracetamol (i.e., 4 g/24 h). Use of paracetamol must be terminated if any liver function tests increase above normal ranges.

Any disease progression that requires other specific antitumor therapy will be cause for discontinuation from the trial.

Anticoagulant Therapy: Patients who are taking warfarin may participate in this trial; however, it is recommended that prothrombin time (international normalized ratio [INR]) is monitored carefully at least once per week for the first month, then monthly if the INR is stable. Subcutaneous heparin is permitted.

Concurrent or procedural medications or therapy given to or taken by the patient will be recorded in the CRF along with the indication. All concomitant medication should be recorded for up to 30 days following the last protocol treatment. After this period, only relevant medication (e.g., medication in patients with treatment-related AEs) will be recorded in the CRF.

Both generic and trade names may be recorded. However, the generic name is generally preferred because of its specificity, whereas trade names are preferred for combination products.

The potential interaction of APR-246 with other medicinal products has not been investigated.

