8.3.4 Progression-free Survival

PFS is defined as the time from randomization to the time of disease progression or relapse (according to RECIST 1.1) or death, or to the date of last tumor assessment without any such event (censored observation) and includes any of the following:

- Occurrence (clinically or imaging signs) of any new lesion
- Increase in measurable and/or non-measurable tumor as defined by the RECIST 1.1 criteria

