9.3 Analysis Populations

The following populations will apply:

Safety Evaluable Population: All patients who received study medication (APR-246 or PLD) will be considered evaluable for safety regardless of the duration of treatment. This population will be used

to summarize all safety parameters.

Efficacy Evaluable Population: All patients with pretreatment measurable disease by RECIST 1.1 who have at least one radiographic assessment after pretreatment or discontinue study medication early due to disease progression and have a p53 mutation will be considered evaluable for efficacy. The efficacy-evaluable population will be the primary analysis population for efficacy.

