9.4.1 Efficacy Data

Overall Response Rate

Best overall response according to RECIST 1.1 will be presented along with the associated exact Clopper-Pearson 2-sided 95% and 1-sided lower 90% binomial confidence limits [20].

Progression-free Survival

PFS is defined as the time from registration to the time of disease progression or relapse (according to RECIST 1.1 only) or death. Patients who do not experience a PFS event will be censored at their last clinic visit contact for the assessment of disease progression.

PFS time will be summarized via a Kaplan-Meier curve with 95% confidence interval. Median PFS will be estimated from the Kaplan-Meier and presented long with 2-sided 95% confidence limits using the method of Brookmeyer and Crowley (1982) [21]. The PFS rate at 3, 6 and 9 months' follow-up will also be presented together with 2-sided 95% confidence limits using the method of Klein (2007) [22].

Evaluation of Biomarkers

The relationship between biomarkers and efficacy in terms of PFS and RECIST response will be explored using logistic regression methodology and accelerated failure time analysis.

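### Section 6.6 takes patients off the trial for any progression needing other therapy, but PFS counts only RECIST progression or death: if scans stop at that point, PFS can be biased upward

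*Combined protocol and SAP*

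**What the plan says.** **Leaving the trial.** Section 6.6: "Any disease progression that requires other specific antitumor therapy will be cause for discontinuation from the trial". The sentence does not mention RECIST, and it speaks of the trial rather than of study treatment. Section 5.3, which lists reasons for stopping APR-246, names RECIST 1.1 progression and, separately, investigator discretion.

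**Scans and follow-up.** Section 4.1, on visits after the end of treatment: "radiological tumor assessments should be performed every 8 weeks until protocol-defined progression occurs". Section 7.2.4 and Table 4 note 6 scan every 8 weeks those who stop therapy without progression; 7.2.4 ends this at radiological progression. Section 7.2.6 also scans 8-weekly until progression, without saying by which criteria. Section 7.2.5 requires a CT or MRI at the end-of-treatment visit, 30 days after the last APR-246 dose. Section 7.2.7 follows survival every 6 months after progression.

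**PFS event and censoring.** Section 9.4.1: "PFS is defined as the time from registration to the time of disease progression or relapse (according to RECIST 1.1 only) or death". It continues: "Patients who do not experience a PFS event will be censored at their last clinic visit contact for the assessment of disease progression". Section 3.1.4 has the same event but a different censoring date: "or the date of last tumor assessment without any such event (censored observation". Section 8.3.4 also censors at the last tumor assessment, but lists as an event: "Occurrence (clinically or imaging signs) of any new lesion".

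**Evaluability.** Section 9.3 accepts patients without a post-baseline scan who "discontinue study medication early due to disease progression and have a p53 mutation will be considered evaluable for efficacy".

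**New therapy.** Table 4 note 11 collects new anticancer treatment during follow-up. No PFS rule uses it.

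**The concern.** A patient may worsen clinically between scans and be moved to another therapy. Read literally, Section 6.6 ends her participation on that ground. Section 9.4.1 gives her a PFS event only if a scan meets RECIST 1.1 or she dies. If no later scan or death is recorded, she is censored, and the reason for the censoring is that she is failing.

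Kaplan-Meier estimation assumes that censored patients have the same outlook as those still followed. Here they would have a worse one, so the median and the 3-, 6- and 9-month rates would be too high. The trial has no control arm in which the same bias could offset, so these figures would be read at face value. The plan has no rule for clinical progression or for the start of new therapy, and no sensitivity analysis that would show the size of the effect.

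**Working it through.** **1. The plan's own figures.** The plan states no PFS assumption (median, hazard or event count), so there is none to reproduce. Its response-rate design figures do reproduce. With X1 ~ Bin(16, p) and X2 ~ Bin(9, p), the probability of rejection is the sum over x ≥ 2 of P(X1 = x)·P(X2 ≥ 5 − x). This gives 9.51% at p = 10% and 90.30% at p = 30% (stated: 9.5% and 90.3%). The Sub-Study, with 14 then 11 patients, gives 9.08% and 89.06% (stated: 9.1% and 89%). PFS enters none of these.

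**2. One patient traced through the sections.** She deteriorates before the first on-study scan and changes therapy.
- 6.6: she leaves the trial.
- 9.3: if she has measurable disease and a p53 mutation, she is efficacy-evaluable without a post-baseline scan, and she is a non-responder.
- 9.4.1: she has no PFS event unless a later scan or death is captured.
- 3.1.4: without such a record she is censored at her last tumor assessment, which is the pretreatment scan. Under 9.4.1 the date is instead her last clinic contact for assessing progression.

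**3. Inputs for the size.** From the documents: scans every 8 weeks (W = 56/30.44 = 1.84 months), an end-of-treatment scan about 30 days after the last dose, n = 25. Assumed, because the documents give neither: a share f of progressions that are clinical only, 10–30%; exponential time to progression with median m = 4 months (3 and 6 checked). Write S(t) = 2^(−t/m), so S(6) = 35.4%.

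**4. Nothing captured after exit, 8-weekly scans, censoring at the last scan.** Let q = 1 − S(W) = 0.273. The Kaplan-Meier factor at each scan is (1 − q)/(1 − f·q), and three scans fall within 6 months. The comparator counts clinical-only progression as an event on its date: (1 − f)·S(3W) + f·S(6), with S(3W) = 38.4%.

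| f | Censored: ((1 − q)/(1 − f·q))³ | Counted as event | Rise, points |
|---|---|---|---|
| 10% | 0.7474³ = 41.8% | 38.1% | 3.6 |
| 20% | 0.7690³ = 45.5% | 37.8% | 7.7 |
| 30% | 0.7919³ = 49.7% | 37.5% | 12.1 |

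(Rises are taken before rounding.)

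**5. Same premise, censoring at the moment of failure.** The curve then estimates the hazard (1 − f)·λ, so the apparent median is m/(1 − f): 4.4, 5.0 and 5.7 months instead of 4.0. The 6-month rate is 2^(−6(1 − f)/4) = 39.2%, 43.5% and 48.3%, a rise of 3.9, 8.2 and 12.9 points.

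**6. A scan one month later documents progression.** The 6-month rate is (1 − f)·S(6) + f·S(5), so the rise is f·(42.0% − 35.4%) = 0.7, 1.3 and 2.0 points. In simulation the median read 4.1 to 4.3 months.

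**7. Other medians and precision.** For m = 3 to 6 months the rise in step 4 runs from 3.4 to 12.1 points and the rise in step 6 from 0.6 to 2.0. Ignoring censoring, the standard error at n = 25 is √(0.354 × 0.646/25) = 9.6 points. The two cases therefore differ from about 1.3 standard errors (12.1/9.6) to about 0.2 (2.0/9.6) at f = 30%.

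**The case against.** A reader might infer that clinical progressors *are* censored as they fail and that PFS *is* inflated. The documents do not support that.

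- Section 7.2.5 requires a scan at the end-of-treatment visit, and 5.3 asks sites to try to complete that visit after a withdrawal. This is where a clinical progressor would most naturally become a RECIST event.
- Sections 4.1, 7.2.4 and 7.2.6 and Table 4 note 6 continue scans after therapy stops. Collecting new anticancer treatment in follow-up implies that follow-up can outlast the switch.
- Death is a PFS event, and 7.2.7 follows survival.
- Section 8.3.4 counts a new lesion found clinically, so some clinical progression is already an event there.
- Sections 8.1 and 5.3 tie progression to RECIST 1.1, so progression in 6.6 may mean no more than that. That 6.6 covers symptomatic or CA-125 progression is a reading of it, not its text.
- Section 9.3 defines a population, not a PFS event. Keeping early progressors in the response denominator is conservative.
- PFS is a descriptive secondary endpoint, and 9.2 defers analysis detail to a SAP due before data lock.

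These points defeat the stronger reading and make step 4 of the check an upper case. They do not close the gap. After withdrawal the end-of-treatment scan is only to be attempted. Section 7.2.4 and Table 4 note 6 cover patients who stopped *without* progression, and 7.2.6 carries no RECIST qualifier. A site that has declared clinical progression and applied 6.6 could reasonably treat scanning as finished, while 4.1 and 7.2.4 point the other way. If scans do continue, PFS is measured partly under later therapy, and the plan has no rule for that either. A promised SAP is a place for the rule; it does not supply one.

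**Conclusion.** The concern stands in conditional form. Section 6.6 conflicts with the follow-up sections over what happens after a progression that needs other therapy, and the PFS rules do not cover clinical progression or new anticancer therapy. If sites follow 6.6 and scans stop, informative censoring biases PFS upward.

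The size depends on what is captured after exit. The 6-month rate rises by about 4 to 12 points if nothing is captured, and by about 0.6 to 2 points if the end-of-treatment scan documents progression. Both ranges rest on an assumed clinical-only share of 10–30% and exponential progression times; the documents fix neither, so they do not establish how large the bias will be. The primary response-rate analysis and its stopping and rejection rules are not affected. The point deserves correction because PFS in an uncontrolled trial will be read at face value and the remedy is small.

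**What to change.** 1. Reconcile Section 6.6 with 4.1, 7.2.4, 7.2.6, 7.2.7 and Table 4, so that it is explicit whether the scheduled scans and survival follow-up continue after such a discontinuation.
2. Use one PFS event definition and one censoring date. Sections 3.1.4 and 8.3.4 use the last tumor assessment, 9.4.1 the last clinic contact; 8.3.4 admits clinically found new lesions, while 3.1.4 and 9.4.1 restrict progression to RECIST 1.1.
3. Keep RECIST-only PFS as the headline, and state how scans after the start of new anticancer therapy are treated in it.
4. Prespecify, in 9.4.1 or in the SAP promised in 9.2, one sensitivity analysis that counts investigator-declared progression leading to discontinuation, or the start of new anticancer therapy, as an event on that date.

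The cost is a few sentences and one extra analysis. The scans are already scheduled, new therapy is already collected, and 5.3 already records the reason and date of withdrawal. PFS will be somewhat lower in the sensitivity analysis.

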6.7 Contraception

Female patients of childbearing potential (defined as < 2 years after last menstruation and not surgically sterile) must use a highly effective method of contraception resulting in a low failure rate (i.e., less than 1% per year) during chemotherapy treatment and for at least 6 months thereafter. These methods of contraception according to the note for guidance on non-clinical safety studies for the conduct of human trials for pharmaceuticals (CPMP/ICH/286/95, modification) include consistent and correct use of hormone containing implants and injectables, combined oral contraceptives, hormone containing IUDs, true sexual abstinence when this is in line with the preferred and usual lifestyle of the subject and partner with vasectomy. Periodic abstinence (e.g., calendar, ovulation, symptothermal, post-ovulation methods), declaration of abstinence for the duration of a trial and withdrawal are not acceptable methods of contraception.

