1. Archived sections from the original formalin fixed paraffin embedded sample reviewed by a gynecological pathologist confirming HGSOE, high grade serous peritoneal cancer or primary fallopian tube cancer and positive immunohistochemistry staining for p53 assessed according to the local methodology (as detailed in the laboratory manual). Cases that do not show p53 staining will not be included.
2. Disease progression between 4 weeks and 6 months after the last platinum-based treatment was administered.
3. At least a single (RECIST 1.1) measurable lesion.
4. Adequate organ function prior to registration:
 - a) Bone marrow reserve
 - Absolute neutrophil count (ANC) $\geq 1.5 \times 10^9/L$

- Platelets $\geq 100 \times 10^9/L$
- Hemoglobin ≥ 9 g/dL
- b) Hepatic
 - Total bilirubin level $< 1.5 \times$ ULN without hepatic metastasis, and $< 4 \times$ ULN with hepatic metastasis
 - Alanine aminotransferase (ALT) and aspartate aminotransferase (AST) $< 2.5 \times$ ULN without hepatic metastasis, and $< 4 \times$ ULN with hepatic metastasis
- c) Renal
 - Calculated creatinine clearance > 30 mL/min calculated per local practice
- d) Electrolytes
 - Potassium within institutional normal ranges.
- 5. Toxicities from previous cancer therapies (excluding alopecia) must have recovered to grade 1 (defined by National Cancer Institute [NCI] Common Terminology Criteria for Adverse Events [CTCAE] version 4.0). Chronic stable grade 2 peripheral neuropathy secondary to neurotoxicity from prior therapies may be considered on a case by case basis by the Principal Investigator.
- 6. If of childbearing potential, negative pretreatment serum pregnancy test.
- 7. If of childbearing potential, willing to use an effective form of contraception (see below) during chemotherapy treatment and for at least 6 months thereafter. Such methods include the following (if using hormonal contraception, this method must be supplemented with a barrier method, preferably male condom):
 - combined (estrogen and progestogen containing) hormonal contraception associated with inhibition of ovulation:
 - oral
 - intravaginal
 - transdermal
 - progestogen-only hormonal contraception associated with inhibition of ovulation:
 - oral
 - injectable
 - implantable
 - intrauterine device (IUD)
 - intrauterine hormone-releasing system (IUS)
 - bilateral tubal occlusion
 - vasectomized partner

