4.4.2 Reference Product PLD

PLD will be supplied by the hospital's pharmacy and will be administered in 28-day cycles.

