4.5 Duration of Therapy

Patients will receive 28-day cycles of PLD chemotherapy with APR-246. Patients may continue to receive APR-246 with PLD for as long as in the Investigator's opinion they are benefiting from treatment and in the absence of disease progression and unacceptable toxicity. After the tenth 28-day cycle, data from assessments conducted within each treatment cycle will no longer be collected, but patients may continue to receive treatment after confirmation from the sponsor.

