5.0 SELECTION AND WITHDRAWAL OF PATIENTS

5.1 Inclusion Criteria

To be eligible to participate in this study, patients must meet all of the following inclusion criteria:

1. Archived sections from the original formalin fixed paraffin embedded sample reviewed by a gynecological pathologist confirming HGSOE, high grade serous peritoneal cancer or primary fallopian tube cancer and positive immunohistochemistry staining for p53 assessed according to the local methodology (as detailed in the laboratory manual). Cases that do not show p53 staining will not be included.
2. Disease progression between 4 weeks and 6 months after the last platinum-based treatment was administered.
3. At least a single (RECIST 1.1) measurable lesion.
4. Adequate organ function prior to registration:
 - a) Bone marrow reserve
 - Absolute neutrophil count (ANC) $\geq 1.5 \times 10^9/L$
 - Platelets $\geq 100 \times 10^9/L$
 - Hemoglobin ≥ 9 g/dL
 - b) Hepatic
 - Total bilirubin level $< 1.5 \times$ upper limit of normal (ULN) without hepatic metastasis, and $< 4 \times$ ULN with hepatic metastasis
 - Alanine aminotransferase (ALT) and aspartate aminotransferase (AST) $< 2.5 \times$ ULN without hepatic metastasis, and $< 4 \times$ ULN with hepatic metastasis
 - c) Renal
 - Calculated creatinine clearance > 30 mL/min calculated per local practice
 - d) Electrolytes
 - Potassium within institutional normal ranges.
5. Toxicities from previous cancer therapies (excluding alopecia) must have recovered to grade 1 (defined by National Cancer Institute [NCI] Common Terminology Criteria for Adverse Events [CTCAE] version 4.0). Chronic stable grade 2 peripheral neuropathy secondary to neurotoxicity from prior therapies may be considered on a case by case basis by the Principal Investigator.
6. If of childbearing potential, negative pretreatment serum pregnancy test.
7. If of childbearing potential, willing to use an effective form of contraception (see below)

during chemotherapy treatment and for at least 6 months thereafter. Such methods include the following (if using hormonal contraception, this method must be supplemented with a barrier method, preferably male condom):

- combined (estrogen and progestogen containing) hormonal contraception associated with inhibition of ovulation:
 - oral
 - intravaginal
 - transdermal
 - progestogen-only hormonal contraception associated with inhibition of ovulation:
 - oral
 - injectable
 - implantable
 - intrauterine device (IUD)

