5.3 Withdrawal of Patients and Study Termination

In accordance with the Declaration of Helsinki, each patient is free to withdraw from the study at any time without penalty or loss of benefits or other adequate treatments to which he/she is otherwise entitled.

Investigators also have the right to withdraw patients from the study in the event of illness, AEs, or other reasons concerning the health or well-being of the patient, or in the case of lack of co-operation. After withdrawal of a patient, the investigator is responsible for ensuring adequate treatment and follow-up, although every effort should be made to complete all assessments at an end-of-treatment visit as listed in Section 7.2.5.

Should a patient decide to withdraw after administration of the IMP, or should the investigators decide to withdraw the patient, all efforts will be made to complete and report the observations up to the time of withdrawal as thoroughly as possible. A complete final evaluation at the time of the patient's withdrawal should be made and an explanation given of why the patient is withdrawing or being withdrawn from the study.

The reason, time and date for withdrawal must be noted in the eCRF. If the reason for withdrawal is a clinical AE, monitoring will continue until the outcome is evident. The specific event must be recorded in the eCRF.

Patients who are withdrawn before completion of the first cycle of APR-246 and PLD as prescribed will be replaced.

The study treatment with APR-246 will be discontinued if any of the following situations occur (in the case of study termination by the Sponsor, patients will be allowed to continue to receive the standard of care):

1. Progressive disease per RECIST 1.1 criteria.
2. The development of toxicity which precludes further study treatment.
3. Patient refusal.
4. Lost to follow-up/noncompliance.
5. Significant illness that can affect the patient's ability to comply with study procedures.
6. At the discretion of the Investigator.
7. Pregnancy.
8. Study termination by Sponsor.

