6.5.2.1 APR-246 Infusion and Systemic PLD Chemotherapy Delays

The Day 1 to 4 APR-246 administration, together with the Day 4 PLD chemotherapy, is to be regarded as one treatment cycle and must not be administered separately.

On Day 1, prior to APR-246 administration, the hematological status of the patient should be assessed. If the patient has any hematological AE that would prevent systemic chemotherapy administration on Day 4, the APR-246 infusion and systemic chemotherapy should be delayed until recovery.

If a patient has any AE on Day 2, 3 or 4 prior to the APR-246 infusion which, in the opinion of the Investigator, would prevent systemic chemotherapy administration, the remainder of the planned APR-246 administration should be stopped. Once the patient has recovered sufficiently to receive chemotherapy, the whole treatment cycle (consisting of Days 1-4 APR-246 and Day 4 chemotherapy) should be restarted as previously planned.

If APR-246 and/or systemic chemotherapy are delayed, the reasons for delay should be recorded in the eCRF.

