6.5.3 Dose Modifications for PLD

For typical hematological and non-hematological AEs seen with PLD the dose modifications should be according to the current summary of product characteristics. However, if any AEs occur that are not typical or that are considered unusual, the Sponsor should be consulted prior to re-treating the patient.

If due to AEs the patient is unable to continue chemotherapy with PLD, the patient may continue monotherapy APR-246 if the following criteria are met:

- Latest radiological scans show evidence of response.
- Patient is evaluated as not having symptoms suggestive of progressive disease.
- The Investigator assessment is that APR-246 monotherapy is of continued benefit to the patient.
- APR-246 administration has been approved by the Sponsor.

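### The contraception period is tied to chemotherapy, which the protocol uses to mean PLD, so for patients continuing on APR-246 alone the required cover shrinks and can lapse during dosing

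*Combined protocol and SAP*

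**What the plan says.** Three places in the protocol set the contraception period, all in the same terms. Inclusion criterion 7, in the synopsis and in section 5.1, requires a patient of childbearing potential to be "willing to use an effective form of contraception (see below) during chemotherapy treatment and for at least 6 months thereafter". Section 6.7 says that such patients "must use a highly effective method of contraception resulting in a low failure rate (i.e., less than 1% per year) during chemotherapy treatment" and for the same six-month minimum afterwards. None of them defines chemotherapy treatment, and none mentions the last dose of APR-246.

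Elsewhere the protocol separates the two drugs. Section 6.5.2.1 describes the "whole treatment cycle (consisting of Days 1-4 APR-246 and Day 4 chemotherapy) should be restarted as previously planned". Section 6.5.3 says that if, because of adverse events, "the patient is unable to continue chemotherapy with PLD, the patient may continue monotherapy APR-246". Four conditions apply: response on the latest scans, no symptoms suggesting progression, benefit in the investigator's judgement, and sponsor approval. There is no limit on the number of monotherapy cycles. Section 4.5 sets no overall limit either; after the tenth cycle "patients may continue to receive treatment after confirmation from the sponsor".

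On pregnancy itself, section 5.3 states: "The study treatment with APR-246 will be discontinued if any of the following situations occur", and lists pregnancy as item 7. Section 7.4.1 repeats that the product must be stopped. It also requires notification within 24 hours of any pregnancy during exposure or in the 30 days after stopping. Table 4 schedules a serum pregnancy test at pretreatment only, and sections 7.2.4 to 7.2.6 list none.

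**The concern.** In the default regimen the choice of anchor makes no difference. APR-246 is given on Days 1 to 4 and PLD on Day 4, so the last doses of both drugs fall on the same day and six months after one is six months after the other.

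The 6.5.3 exception breaks that link. Section 6.5.3 itself describes a patient whose chemotherapy has ended while APR-246 goes on. If chemotherapy means PLD, her six months start while she is still receiving the investigational drug, and every further cycle uses some of them up. With enough cycles she would be receiving APR-246 with no contraception requirement in force.

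The protocol plainly treats pregnancy on APR-246 as something to avoid. With no pregnancy test scheduled after entry, prevention depends on this one rule. What is at stake is the safety of a few patients. The response rate, PFS, the two-stage decision rule and the analysis populations are not affected.

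**Working it through.** The plan states no figure on this point, so there is none to reproduce. The check is calendar arithmetic.

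**Inputs from the protocol**
- Cycle length 28 days (6.3; section 4.4.2 says of PLD "and will be administered in 28-day cycles").
- APR-246 on Days 1 to 4, PLD on Day 4 (6.3, 6.4).
- Contraception for at least six months after chemotherapy treatment (synopsis, 5.1 item 7, 6.7).
- No cap on monotherapy cycles (6.5.3, 4.5).

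**Assumptions**
- Six months is 183 days, with 181 to 184 as the range.
- Cycles run on time.
- Chemotherapy means PLD.

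**Set-up.** Let day 0 be the last PLD dose, which is Day 4 of the last combined cycle. Monotherapy cycle k is then dosed on days 28k − 3 to 28k. The text does not say when chemotherapy treatment ends, so there are two start points:
- A, the last PLD dose: the requirement ends on day 183, and cover after the last APR-246 dose is 183 − 28k.
- B, Day 28 of the last PLD cycle, which is day 24: the requirement ends on day 24 + 183 = 207, and cover is 207 − 28k.

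| Monotherapy cycles (k) | Dosing days | Cover under A (days) | Cover under B (days) |
|---|---|---|---|
| 1 | 25 to 28 | 155 | 179 |
| 3 | 81 to 84 | 99 | 123 |
| 5 | 137 to 140 | 43 | 67 |
| 6 | 165 to 168 | 15 | 39 |
| 7 | 193 to 196 | −13 | 11 |
| 8 | 221 to 224 | −41 | −17 |

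**Lapse during dosing.** Under A, cycle 7 starts on day 193, which is 193 − 183 = 10 days after the requirement ends. Under B, cycle 8 starts on day 221, which is 221 − 207 = 14 days after it ends.

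**Length of six months.** With 181 to 184 days, A ends on days 181 to 184, always before cycle 7. B ends on days 205 to 208, always after cycle 7 and before cycle 8. The cycle numbers do not change.

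**Delays.** A cumulative delay of 19 days moves the start of cycle 6 to day 165 + 19 = 184, past the end under A. A delay of 15 days moves the start of cycle 7 to day 193 + 15 = 208, past the end under B. Either brings the lapse forward by one cycle.

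**Patients affected.** The documents give neither the share of childbearing potential nor the share moving to monotherapy. Assuming 0 to 10% and 5 to 20%, with 25 patients (Main Study) to 50 (Main Study plus Sub-Study):
- lower: 25 × 0 × 0.05 = 0;
- upper: 50 × 0.10 × 0.20 = 1.

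The upper value needs both shares at their maximum, and it counts anyone who starts monotherapy, not only those who reach a 7th cycle.

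**With the period tied to the last dose of either drug,** required cover after the last APR-246 dose is at least six months for every k.

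**The case against.** The strongest objection is that the gap depends on an undefined term. Section 6.5.2.1 also says that the two drugs form one treatment cycle and are not to be given separately, so a site could take chemotherapy treatment to mean the whole regimen. On that reading there is no gap. This stands as a limit on the claim. It does not remove the problem, because the sentence in 6.5.3 that creates the exception uses chemotherapy for PLD alone.

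The route to an actual lapse is also narrow. Monotherapy requires a response on the latest scans, and the first on-study scan is at the end of Cycle 2. The 7th monotherapy cycle is therefore unlikely before overall Cycle 9, and the 8th before Cycle 10. If PLD stops after Cycle 4, the 7th is Cycle 11, by which point section 4.5 requires sponsor confirmation as well. The patient must not be surgically sterile (6.7), in a disease whose first-line management includes debulking surgery (2.2). She must also stay free of progression on APR-246 alone for about six months. All of this stands and settles the size of the point.

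A reader might infer that the protocol gives too little cover after APR-246. The documents do not support that. The toxicology section is redacted and the Investigator's Brochure is not supplied, so the period needed is unknown. The 30 days in 7.4.1 is a reporting window and cannot serve as a contraception standard. Up to five on-time monotherapy cycles leave at least 43 days of required cover, and nothing available shows that to be too short. The six months is also a minimum, so the figures describe what is required, not what patients will do.

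**Conclusion.** The point holds for one exception and is minor. For the default regimen the rule covers both drugs. For APR-246 monotherapy under 6.5.3, with chemotherapy read as PLD, the required cover after the last APR-246 dose falls by 28 days with each on-time cycle. The requirement would lapse during dosing from about the 7th monotherapy cycle, counted from the last PLD dose, or the 8th, counted from the end of the last PLD cycle.

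This rests on the reading of an undefined term, on cycles without delay and on six months of 181 to 184 days. The number of patients affected is 0 to 1 under the assumed shares and probably near 0; a lapse while APR-246 is being given would be rarer still. It would go too far to conclude that patients will be dosed unprotected, or that cover after APR-246 is inadequate in general. The supportable conclusion is that a safety rule is tied to the wrong event for a pathway that the protocol itself allows.

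**What to change.** In the synopsis (inclusion criterion 7), 5.1 item 7 and 6.7, state the period as: during study treatment (PLD or APR-246) and for at least 6 months after the last dose of either, whichever is later. If the sponsor's non-clinical data support a different period for APR-246, state that period instead.

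The cost is a wording change in three places, with no new visit, test or patient. The consent form was not available for review. It should be checked, and changed only if it ties the period to chemotherapy in the same way.
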